12.0 Statistical Considerations

12.1 Study Endpoints

12.1.1. Rate of late GI and GU toxicities \geq grade 3 (see Appendix for scoring scheme)

12.1.2. Three-year actuarial rate of freedom from biochemical failure.

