12.2. Sample Size

12.2.1. Sample Size

12.2.1.1. Phase I Component: Between 1990 and 2007, we have treated 4260 patients with early stage prostate cancer (clinical stage T1 or T2, initial PSA <10 ng/ml, KPS 90 or 100) with protons only. The 3-year actuarial rectal/urinary grade 3 toxicity rate was $0.69\% \pm 0.15\%$ SE in this cohort. We will conservatively assume the standard toxicity rate p_0 to be 1% and set the unacceptable toxicity rate p_1 at 5%. Statistical error rates will be set at $\alpha=10\%$ for a false positive result (calling the treatment too toxic when it is not) and $\beta=10\%$ for a false negative result (accepting that the treatment is not too toxic when in reality it is) when using a one-sided test of significance. The sample size meeting these requirements is 105 patients.

12.2.1.2. Phase II Component: In the same patient cohort, the 3-year actuarial rate of biochemical progression free survival (bPFS) was 96%. We will conservatively assume the standard 3-year biochemical failure rate p_0 to be 5% and set the unacceptable failure rate p_1 at 10%. Statistical error rates for false positive and false negative results will again be set at 10%. The required sample size is 187 patients, which exceeds the required sample size for the toxicity endpoint. An additional 35% will be added to this number to guard against ineligible or evaluable cases, resulting in 288 patients. In order to be conservative the sample size for the Phase I/II study will be set to 300 patients.

12.2.1.3. Assuming we accrue the target goal of 187 evaluable patients, a 5% late toxicity rate equates to 9.34 patients with toxicity. If we have 9 or fewer patients with toxicity, the protocol therapy will be considered for further study. In addition, we must also meet the goals for tumor control. Assuming the target goal of 187 patients, tumor control will be considered acceptable if 12 or fewer patients have biochemical failure within the first three years. For the protocol therapy to be recommended for further study, both the toxicity and tumor control outcomes must be considered acceptable. This equates to 9 or fewer patients with late toxicity, and 12 or fewer patients with recurrence. If the study accrues more or less than 187 evaluable patients, these cut-off numbers will be adjusted accordingly.

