12.5.3 Analysis and Reporting of Final Treatment Results (10/29/01)

The analysis to report the final results of treatment will be undertaken when each patient has been potentially followed for a minimum of 3 years. The emphasis of this analysis will be on biochemical control. The usual components of this analysis are:

- patients excluded from the analyses with their reasons for exclusion
- distribution of the important baseline prognostic variables
- patient accrual rate
- observed results with respect to the endpoints described in Section 12.1.

References

1. Hanks, G.E., et al., *PSA confirmation of cure at 10 years of T1B, T2, N0, M0 prostate cancer patients treated in RTOG protocol 7706 with external beam irradiation*. Int J Radiat Oncol Biol Phys, 1994. **30**(2): p. 289-92.
2. Brenner, D.J. and E.J. Hall, *Fractionation and protraction for radiotherapy of prostate carcinoma*. Int J Radiat Oncol Biol Phys, 1999. **43**(5): p. 1095-101.
3. Zietman, A., et al., *The Patterns of Care Survey of radiation therapy in localized prostate cancer: similarities between the practice nationally and in minority-rich areas*. Int J Radiat Oncol Biol Phys, 2001. **50**(1): p. 75-80.
4. Zietman, A.L., et al., *Comparison of conventional-dose vs high-dose conformal radiation therapy in clinically localized adenocarcinoma of the prostate: a randomized controlled trial*. JAMA, 2005. **294**(10): p. 1233-9.
5. Zelefsky, M.J., et al., *High-dose intensity modulated radiation therapy for prostate cancer: early toxicity and biochemical outcome in 772 patients*. Int J Radiat Oncol Biol Phys, 2002. **53**(5): p. 1111-6. 1125: Hurwitz MD, et al. Lack of radiation dose response...[PMID:12128108]Related Articles, Books, LinkOut.
6. Fowler, J.F., et al., *What hypofractionated protocols should be tested for prostate cancer?* Int J Radiat Oncol Biol Phys, 2003. **56**(4): p. 1093-104.
7. Brenner, D.J., et al., *Direct evidence that prostate tumors show high sensitivity to fractionation (low alpha/beta ratio), similar to late-responding normal tissue*. Int J Radiat Oncol Biol Phys, 2002. **52**(1): p. 6-13.
8. King, C.R. and J.F. Fowler, *Yes, the alpha/beta ratio for prostate cancer is low or "methinks the lady doth protest too much...about a low alpha/beta that is"*. Int J Radiat Oncol Biol Phys, 2002. **54**(2): p. 626-7; author reply 627-8. 658: Hoogeman MS, et al. A model to simulate day-to-day...[PMID:12243842]Related Articles, Books, LinkOut.

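### The cut-off of 12 or fewer biochemical failures in 187 carries a 14.6% false-positive rate, not the stated 10%; the design behind n = 187 has a cut-off of 13

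*Combined protocol and SAP*

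**What the plan says.** Section 12.2.1.2 starts from the institution's own cohort, in which "the 3-year actuarial rate of biochemical progression free survival (bPFS) was 96" per cent, and then rounds the failure rate up: "We will conservatively assume the standard 3-year biochemical failure rate p_0 to be 5" per cent. The unacceptable rate is 10%. On the errors it says: "Statistical error rates for false positive and false negative results will again be set at 10" per cent. The resulting sample size is 187 evaluable patients, and enrolment is set at 300 to allow for losses.

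Section 12.2.1.3 turns this into a count: "tumor control will be considered acceptable if 12 or fewer patients have biochemical failure within the first three years". It repeats the figure when it combines the two endpoints: "This equates to 9 or fewer patients with late toxicity, and 12 or fewer patients with recurrence". Both endpoints must pass for the regimen to go forward. For other sample sizes it says only: "If the study accrues more or less than 187 evaluable patients, these cut-off numbers will be adjusted accordingly".

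Section 12.1.2 defines the endpoint as "Three-year actuarial rate of freedom from biochemical failure", and section 12.5.3 places the final analysis at the point "when each patient has been potentially followed for a minimum of 3 years".

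**The concern.** A single-arm design fixes its sample size and its cut-off together: the error rates belong to the pair. The plan gives the error rates and the sample size in one paragraph and the cut-off in the next, with no derivation of the cut-off and no operating characteristics for it. If 12 is not the cut-off that goes with 187, the error rates claimed for the tumour-control decision are not those of the rule that will be applied.

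The two versions differ when exactly 13 failures are seen. The written rule then rejects the regimen, while the design that produced 187 accepts it. That should be settled before the data are known. The cut-off of 12 is also the base from which any adjustment would start, and with 300 to be enrolled the evaluable number may well not be 187.

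**Working it through.** **Inputs (section 12.2.1).** Acceptable failure rate p0 = 5%; unacceptable rate p1 = 10%; both errors 10%; n = 187; accept if X ≤ 12. Section 12.2.1.1 defines a false positive as condemning an acceptable treatment and specifies a one-sided test. I carry both over to the biochemical endpoint, because section 12.2.1.2 says the errors are set in the same way again.

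**Formulas.** With X ~ Binomial(n, p) and a rule that accepts if X ≤ c:

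- false-positive rate = P(X > c | p0)
- false-negative rate = P(X ≤ c | p1)

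**Reproducing the plan's sample sizes.** I searched for the smallest n at which some c keeps both errors at or below 10%.

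- 5% against 10%: nothing qualifies up to n = 186. The first design is n = 187 with c = 13. This is the plan's 187.
- 1% against 5% (toxicity): the first design is n = 105 with c = 2 (8.9% / 9.9%). This is the plan's 105.

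The one-sample normal approximation gives 177 for the biochemical endpoint, the continuity-corrected version 196 and the arcsine version 178. Only the exact binomial gives 187, so it is very probably the method used.

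**Errors at n = 187.**

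| Accept if | False positive at 5% | False negative at 10% |
|---|---|---|
| 12 or fewer (as written) | 14.6% | 5.9% |
| 13 or fewer | 8.7% | 9.8% |
| 14 or fewer | 4.9% | 15.2% |

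Only 13 meets both limits. The normal-approximation boundary points the same way: 187 × 0.05 + 1.2816 × √(187 × 0.05 × 0.95) = 9.35 + 3.82 = 13.17.

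**Could 12 be right on another reading?**

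- *Another sample size.* With c = 12 the false-positive rate is within 10% only for n ≤ 174 (at 174: 9.8% / 10.4%), and the false-negative rate only for n ≥ 175 (at 175: 10.1% / 9.9%). No n meets both.
- *An approximation.* At n = 187 and c = 12 the false-positive rate is 14.5% with continuity correction and 11.0% without. Both exceed 10%.
- *Error labels swapped.* One of the two errors is still 14.6%.

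**Practical size.** At a true failure rate of 4% (100% − 96%), the rejection probability is 3.9% with c = 12 and 1.9% with c = 13.

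**Evaluable numbers other than 187.** c = 13 meets both limits for n = 187–191 and c = 14 for n = 199–207. Between 187 and 300, no cut-off meets both at n = 192–198 or 208–209. At n = 195, for example, c = 13 gives 11.2% / 7.0% and c = 14 gives 6.6% / 11.3%.

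**The case against.** The best defence is that 12 was a deliberate, stricter choice on a different basis. Twelve is the largest count in 187 whose simple normal-approximation 95% upper limit stays below 10%:

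- 12/187 = 6.42%, standard error √(0.0642 × 0.9358 / 187) = 1.79%, upper limit 6.42 + 1.96 × 1.79 = 9.93%
- 13/187 = 6.95%, standard error 1.86%, upper limit 10.60%

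The paragraph after section 12.2.1.3 argues for toxicity in a similar way, by setting an upper confidence limit against the highest rate the investigators would accept. On this view, moving to 13 lowers the bar for efficacy. The effect is also modest: the error is on the cautious side, the 14.6% applies at a p0 the plan itself calls conservative, the outcome is only a recommendation for further study, and the cut-off changes if the evaluable number is not 187.

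Part of this stands. The direction is conservative and the effect moderate, and the sponsor may prefer 12. But the plan nowhere gives the confidence-limit argument for biochemical failure, and that argument would not bring the false-positive rate back to 10%. Section 12.2.1 uses the word conservative for p0 and for rounding the enrolment up, not for this cut-off. The adjustment clause does not help either: the mismatch exists at exactly 187, and the clause names no method.

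**Conclusion.** The inconsistency is real. As written, the tumour-control rule has error rates of 14.6% and 5.9%, not 10% and 10%. The cut-off that belongs to the stated design is 13 or fewer, at 8.7% and 9.8%. The excess false-positive risk at p0 is 4.6 percentage points over the stated limit, and protection against a regimen with 10% failure is better than stated. It should be corrected because the count decides half of the recommendation, but it does not undermine the trial.

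The figures assume that all 187 patients have known three-year status and that the one-sided test stated for toxicity carries over. The endpoint is an actuarial rate and follow-up is only potentially three years, so censoring would change the errors. The documents give no censoring rate from which to say by how much.

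**What to change.** In section 12.2.1.3, do one of the following:

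- change 12 to 13 in both places; or
- keep 12, state why, and replace the 10% error rates for this endpoint with 14.6% (false positive) and 5.9% (false negative).

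Replace the open-ended adjustment clause, for this endpoint, with a rule: the cut-off is recomputed from the exact binomial with p0 = 5% and p1 = 10% at the evaluable number reached, and the achieved errors are reported. Name the error that is held at or below 10% when no cut-off meets both limits. At n = 195, holding the false-negative rate gives 13 and holding the false-positive rate gives 14. It would also help to add a sentence on how patients censored before three years enter the count.

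The cost is one number in two places and two or three sentences, with no change to sample size, visits or treatment. The price of moving to 13 is that false acceptance at 10% failure rises from 5.9% to 9.8%, still within the stated limit. The price of keeping 12 is a stated false-positive rate above 10%.

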With a sample size of 187 patients and an assumed late toxicity rate of 2%, we have an upper = 95% confidence limit of 5% for (grade ≥ 3) late toxicity. This upper bound corresponds to the limit we would accept in terms of toxicity.

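### The tumor-control endpoint and both benchmarks are 3-year actuarial rates, but Section 12.2.1.3 decides on raw counts among undefined evaluable patients, with no time limit on the toxicity count

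*Combined protocol and SAP*

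**What the plan says.** - **Endpoints.** Section 12.1.2: "Three-year actuarial rate of freedom from biochemical failure". Section 12.1.1 is the rate of late GI and GU toxicity of grade 3 or higher, with no time horizon. It refers to an Appendix for scoring, which is not in the supplied text.
- **Benchmarks.** Section 12.2.1.1: "The 3-year actuarial rectal/urinary grade 3 toxicity rate was" 0.69%. Section 12.2.1.2: "the 3-year actuarial rate of biochemical progression free survival (bPFS) was 96" per cent. From these the plan sets p0 = 1% and p1 = 5% for toxicity, and p0 = 5% and p1 = 10% for biochemical failure, with both error rates at 10%.
- **Sample size.** 187 patients, then "An additional 35% will be added to this number to guard against ineligible or evaluable cases, resulting in 288 patients", rounded up to 300.
- **Decision rule (12.2.1.3).** For tumor control, "tumor control will be considered acceptable if 12 or fewer patients have biochemical failure within the first three years". For toxicity, "If we have 9 or fewer patients with toxicity, the protocol therapy will be considered for further study". Both are set per 187 evaluable patients, and "If the study accrues more or less than 187 evaluable patients, these cut-off numbers will be adjusted accordingly".
- **Analysis.** Section 12.5.3 places the final analysis after at least 3 years of potential follow-up for each patient. It reports the 12.1 endpoints and lists exclusions with reasons. Toxicity visits continue beyond 3 years (11.1, footnote c).

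**The concern.** A count equals an actuarial rate only when every patient's 3-year status is known. Section 12.5.3 removes administrative censoring before 3 years, so the gap comes from drop-out, death and missed assessments. The decision rule does not say what happens to a patient who leaves event-free at, say, 18 months. Kept in the denominator, he counts as a success, and the rule leans towards acceptance. Dropped as not evaluable, he is removed while a patient who failed at 18 months stays, and the rule leans towards rejection. The same data could then pass or fail according to how one undefined word is read.

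The adjustment clause will almost certainly be needed, because 300 patients are enrolled against a target of 187 evaluable. For toxicity, the benchmark stops at 3 years but the count does not.

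**Working it through.** **1. The plan's own figure.** The smallest exact one-stage binomial design with P(X > c | 5%) ≤ 10% and P(X ≤ c | 10%) ≤ 10% is n = 187 with c = 13 (errors 8.7% and 9.8%). So 187 reproduces as a fixed-denominator design with every 3-year status known. With the written cut-off of 12 the errors are 14.6% and 5.9%. That shift is a separate cut-off question, so results for 13 are also shown. The inflation also reproduces: 187/0.65 = 287.7, or 288.

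**2. Loss model (assumption).** Failure and loss are exponential and independent. With 3-year failure p and 3-year loss L:
- hf = −ln(1−p)/3 and hl = −ln(1−L)/3
- observed failure proportion, lost patients kept: C = hf/(hf+hl) × [1 − exp(−3(hf+hl))]
- completers only: C / [C + (1−p)(1−L)]

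Example, p = 5%, L = 20%: hf = 0.0171, hl = 0.0744, and exp(−3(hf+hl)) = 0.95 × 0.80 = 0.76. Then C = 0.187 × 0.24 = 0.0449, and completers only = 0.0449/(0.0449 + 0.76) = 0.0557.

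The documents give no loss rate. The nearest figure, the 35% allowance, mixes ineligible with non-evaluable cases and serves only as an outer limit.

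**3. Lost patients dropped, 187 evaluable: probability of rejection**

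| True 3-year failure | Cut-off | L=0 | 10% | 20% | 35% |
|---|---|---|---|---|---|
| 5% (p0) | ≤12 | 14.6% | 18.8% | 24.5% | 37.3% |
| 5% (p0) | ≤13 | 8.7% | 11.8% | 16.2% | 26.9% |
| 4% (observed) | ≤12 | 3.9% | 5.4% | 7.7% | 13.9% |

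With ≤13, the 10% limit at p0 is passed at about 4.5% loss.

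**4. Lost patients kept as successes: probability of accepting a true 10%**

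At L = 0, 10 and 20% the observed proportion is 10.0, 9.5 and 9.0%. P(X ≤ 12 of 187) is 5.9, 9.0 and 13.4%. With cut-offs scaled in proportion (12/187 × 234 = 15.0; 12/187 × 300 = 19.3, so 19), 20% loss gives 10.0% for 15/234 and 6.1% for 19/300. At 35% loss these become 19.8% and 14.6%.

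**5. Both readings on the same trials.** 40,000 simulated trials, 234 starters (about 0.805 × 234 = 188 evaluable at 20% loss), true 5%, acceptance if failures/denominator ≤ 12/187. The readings give opposite decisions in about 7, 13 and 22 to 23% of trials at 5, 10 and 20% loss. At 20% loss, acceptance is about 94% (kept) against 71% (dropped).

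**6. Toxicity window.** No loss, constant hazard, uniform 13-month accrual (12.4), final analysis as soon as 12.5.3 allows, so follow-up runs from 3 to about 4.1 years. P(X ≤ 9 of 187):

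| True 3-year rate | Counted to 3 years | Counted to analysis date |
|---|---|---|
| 1% | >99.9% | >99.9% |
| 2% | 99.5% | 98.6% |
| 3% | 94% | 87% |
| 5% | 54% | 34% |

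The 54% itself comes from the choice of 9 as cut-off, not from the window.

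**The case against.** Much of the case for leaving the rule alone is sound.

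- **Follow-up and reporting.** Section 12.5.3 secures 3 years of potential follow-up, reports the actuarial endpoint, and lists exclusions with reasons. A reader might infer that patients would be analyzed before reaching 3 years, or that no actuarial analysis is planned. Neither is so. Only the decision rule departs from the endpoint.
- **Harm to a regimen as good as the standard.** A reader might infer from the 18.8% and 24.5% that dropping lost patients would often reject such a regimen. The documents do not support this. Those figures apply at p0 = 5%, set deliberately above the observed 4%. At 4%, false rejection stays below 10% up to 20% loss.
- **Keeping lost patients.** With 234 or 300 patients and 20% loss, this reading meets the planned 10%.
- **Which reading is meant.** The inflation for non-evaluable cases hints at dropping, but ineligibility alone could account for much of the 35%. No section prescribes either reading.
- **Adjustment.** The toxicity cut-off is shown as 5% of 187, so proportional scaling is a natural reading there, though it is not stated.
- **Toxicity window.** A reader might infer that the open window makes that decision arbitrary. At p0 = 1% it changes almost nothing. At 5%, the rate the plan calls unacceptable, it moves the decision towards rejection, which is correct.

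What stands is that the text does not choose between the two readings, and their decisions diverge as loss rises.

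**Conclusion.** The point holds as an under-specified decision rule that does not match its own endpoint and benchmarks. It should be corrected, but it does not invalidate the design. Its weight depends on a loss rate that the documents do not give, and on exponential, independent failure and loss.

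At 10 to 20% loss and a true 5% failure rate, the two readings disagree in roughly one trial in eight to one in four or five. The error limits are exceeded mainly in two cases: at p0 when lost patients are dropped, and at a true 10% when they are kept with only 187 patients. Below about 5% loss the effect is small. The toxicity window needs stating, but on the plan's own hypotheses it is a minor matter. It rests on the supplied text, since the scoring Appendix was not available.

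**What to change.** In Section 12.2.1.3:

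- Base both decisions on the 3-year Kaplan-Meier estimate in all eligible patients who started protocol radiotherapy, censoring at the last PSA or last toxicity assessment.
- Count late grade ≥3 toxicity only to 3 years, and state one time origin that matches the historical benchmark.
- Compare each estimate with the cut-off as a proportion: currently 12/187 and 9/187, or whatever values are settled when the cut-offs themselves are reviewed. This works for any number of patients and replaces the open adjustment clause.
- Confirm that the 96% benchmark uses the same event: Phoenix or ASTRO (11.4.1 uses ASTRO for institutional comparison), and deaths counted or censored (it is labelled progression-free survival).
- Report cumulative incidence with death as a competing event as a sensitivity analysis.

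**Cost.** SAP wording and standard survival analysis, with no new trial data; a mismatch in the benchmark's event definition would need resolving. With 187 patients and a true 10% rate, simulation puts false acceptance against 12/187 at about 5 to 7% across 0 to 35% loss. False rejection at 5% is about 15 to 20% at 0 to 20% loss, or about 9 to 13% against 13/187.

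**If an upper-bound rule is preferred.** The last paragraph of Section 12.2 already points that way for toxicity ("This upper bound corresponds to the limit we would accept in terms of toxicity", at 95%). Adopt it only together with a cut-off correction, and state one confidence level. A one-sided 90% bound with complete follow-up allows at most 5 of 187 toxicities. At the 2% rate assumed in that paragraph it would reject 17.4% of the time, against 0.5% with the present cut-off of 9.

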12.3. Stopping Rules for Excessive Acute Effects

The acute toxicity rate ($>=$ grade 2) in our previously treated patient with early stage prostate cancer was less than 15% (12.6% grade 2, 0.8% grade 3). We wish to ensure that the hypofractionation treatment does not increase the acute toxicity rate within the first three months after treatment commenced. The following table

gives the numbers of patients with acute toxicity (\geq grade 2) that are considered unacceptable at interim check points as calculated by the method of Fleming. For example, if there are 17 or more acute toxicities reported in the first 50 patients, the accrual will be stopped and the treatment protocol will receive a special review. Note that these are the first 50 patients entered (and eligible) consecutively onto the trial and not the first 14 patients for whom we have collected data up to three months. The last column lists the power to detect a 10% increase from an assumed 15% toxicity rate to 25% based on the number of patients available at each stage.

Number of Patients with acute Toxicity	Number of Patients Available	Power (%) (1- β)
15	50	20.7
22	100	75.6
30	150	92.1
35	187	97.6

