12.5 Analysis Plan

12.5.1 Interim Analyses of Accrual and Toxicity Data

- Interim reports will be prepared every six months until the final analysis. In general, the interim reports include information about:
 - accrual rate with projected completion date
 - Pre-treatment characteristics of patients accrued
 - frequency and severity of toxicity.

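### Section 12.3 pools acute grade 2 with grade 3+ in its only accrual-stopping rule, so a several-fold excess of acute grade 3+ toxicity could go undetected

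*Combined protocol and SAP*

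**What the plan says.** Section 12.3 covers acute events in the first three months after treatment begins. It states that the acute rate of grade 2 or higher in earlier patients "was less than 15% (12.6% grade 2, 0.8% grade 3"). Its table "gives the numbers of patients with acute toxicity (\geq grade 2) that are considered unacceptable at interim check points", by Fleming's method: 15 of 50, 22 of 100, 30 of 150 and 35 of 187. The last column is the "power to detect a 10% increase from an assumed 15% toxicity rate to 25" per cent. Reaching a count stops accrual and leads to a special review. The worked example in the text differs from the table: "if there are 17 or more acute toxicities reported in the first 50 patients, the accrual will be stopped".

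No other section sets an action threshold for toxicity during accrual:

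- Section 12.2.1.1 sets 1% as the standard and 5% as the unacceptable grade 3 rate, but for the late endpoint (the supporting figure is a 3-year actuarial rate).
- Section 12.2.1.3 judges late toxicity at the end: 9 or fewer of 187 is acceptable.
- Section 12.5.1 asks for six-monthly reports that include "frequency and severity of toxicity", with no threshold and no action.
- Section 12.4 calls for re-evaluation only if accrual is slow.

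**The concern.** The primary objective (Section 2.1) and the first endpoint (Section 12.1.1) are about toxicity of grade 3 or higher. The interim rule does not separate that severity from grade 2. Since 12.6 of the 13.4 percentage points in the historical rate are grade 2 (12.6/13.4 = 94%), the boundary is driven almost wholly by grade 2. A shift from grade 2 to grade 3+ leaves the count unchanged, and a several-fold rise in grade 3+ adds only a few points to the pooled rate. At stake is the protection of patients still to be enrolled: accrual could continue through several checks while severe acute toxicity ran well above its historical level.

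**Working it through.** **Inputs.** From Section 12.3: boundaries 15/50, 22/100, 30/150 and 35/187; null 15%, alternative 25%; historical acute rates 12.6% (grade 2) and 0.8% (grade 3). From Section 12.2.1.1: late rates 0.69% observed and 1% assumed. From Section 12.4: 13 months of accrual. Assumption: in the second scenario below, grade 2 stays at 12.6% while grade 3+ rises.

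**Step 1: reproduce the plan's power.** Normal approximation at each look, without continuity correction: power = 1 − Φ[(r − 0.25n)/√(n × 0.25 × 0.75)]. For r = 15, n = 50: (15 − 12.5)/3.062 = 0.816, giving 20.7%. The other looks give 75.6%, 92.1% and 97.6%. All four match the table. Exact binomial values are 25.2%, 78.9%, 93.7% and 98.3%. A first boundary of 17 would give 7.1% by the same formula, so the printed 20.7% was computed from 15.

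**Step 2: stopping probability of the pooled rule.** Let X(n) be the pooled count among the first n patients, binomial with pooled rate p. The cumulative probability of stopping is 1 − P[X(50) ≤ 14, X(100) ≤ 21, X(150) ≤ 29, X(187) ≤ 34], computed exactly over the sequence of looks.

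*Severity shift, pooled rate unchanged.* With p = 12.6% + 0.8% = 13.4%, the cumulative values are 0.2%, 1.3%, 2.2% and 3.5%. Only p enters, so these hold for any mix of grade 2 and grade 3+.

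*Grade 2 at 12.6%, grade 3+ raised:*

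| Acute grade 3+ | Multiple of 0.8% | Pooled p | By 50 | By 100 | By 150 | By 187 |
|---|---|---|---|---|---|---|
| 5% | 6.25 | 17.6% | 2.2% | 15.6% | 27.9% | 40.6% |
| 8% | 10 | 20.6% | 7.5% | 40.7% | 63.1% | 78.4% |
| 10% | 12.5 | 22.6% | 14.0% | 59.9% | 82.0% | 92.4% |

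At 5%, the expected pooled counts (n × 0.176) are 8.8, 17.6, 26.4 and 32.9, each below its boundary. With 17/50 at the first look, the first column becomes 0.4%, 1.9% and 4.4%; the values by 187 hardly change (40.5%, 78.3% and 92.4%).

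**Step 3: what a separate boundary could do (illustration only).** Acute grade 3+ counts of 3/50, 4/100, 5/150 and 5/187, by the same exact method:

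| True acute grade 3+ | By 50 | By 100 | By 150 | By 187 |
|---|---|---|---|---|
| 5% | 46% | 76% | 89% | 96% |
| 1% | 1.4% | 2.6% | 3.4% | 5.3% |
| 0.8% | 0.8% | 1.3% | 1.7% | 2.5% |

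**Step 4: late events on the same boundary.** Adding the late rate to the acute rate gives 0.8% + 0.69% = 1.49% to 0.8% + 1% = 1.8%. The illustrative boundary then triggers in about 17% to 27% of trials with nothing amiss. This is an upper range, because it treats every late event as observed by the time of the look.

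**The case against.** Pooling grade 2 and above is a legitimate design choice for a rule on acute effects. It guards against a general rise in acute toxicity, and every grade 3+ event counts toward it. Patients are also examined weekly during treatment (Sections 6.4.1 and 11.2.1), and the six-monthly reports cover severity. Section 1.4 reports 62 patients treated at 60 Gy in 20 fractions with no grade 3+ complication at a minimum of one year. That is reassuring but does not settle the matter: the exact one-sided 95% upper limit for 0 of 62 is 1 − 0.05^(1/62) = 4.7%.

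Three stronger readings are tempting, and the documents do not support them.

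- *That a large excess would not stop accrual.* By count, 14 of the first 50 patients could all have grade 3+ events without crossing the table boundary, where 0.8% predicts 0.4. But a true pooled rate of 28% would stop accrual with 93% probability by 100 patients, and the table in Step 2 shows 78% and 92% by 187 at grade 3+ rates of 8% and 10%.
- *That accrual could run on at an acute rate the plan itself calls unacceptable.* The 1% and 5% in Section 12.2.1.1 belong to late toxicity. The plan sets no unacceptable rate for acute grade 3+; 5% is used here only as a scenario.
- *That the safety component protects no enrolled patient, because late toxicity is judged only at the end.* The acute rule does give protection. Judging late toxicity after accrual follows largely from timing: the rate is a 3-year one and accrual is projected at 13 months, so few late events could appear in time under any rule.

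**Conclusion.** The point holds in limited form. The only accrual-stopping rule cannot see severity, and an acute grade 3+ rate about six times historical would more likely than not pass all four checks (41% chance of stopping by 187 patients, 2.2% at 50). A pure shift from grade 2 to grade 3+ would almost never be caught (3.5%). Excesses of ten-fold or more are usually caught, but late. The first result assumes that grade 2 stays at 12.6%; both assume independent patients with a constant rate and use the table's boundaries. This is a gap in sensitivity, not an arithmetic error: the plan's power figures reproduce. It is a change to consider rather than one that must be made. The disagreement between 17 and 15 of 50 is a separate inconsistency that does need reconciling.

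**What to change.** Add a column to the Section 12.3 table with a separate boundary for acute grade 3+ GI/GU toxicity at 50, 100, 150 and 187 patients, leading to the same accrual stop and special review. Base it on the historical acute 0.8% (about 1%) and on an unacceptable acute rate that the sponsor chooses and states. The counts in Step 3 show only that such a boundary is feasible; the sponsor sets the final ones.

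Do not count late grade 3+ events on this boundary: Step 4 shows what that does to false triggers, for little gain within the accrual period.

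Reconcile the first-look count between the text and the table, and state the power that belongs to the count retained.

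The cost is one table column and a sentence. Toxicity evaluations are already scheduled (Section 11.1) and severity is already reported. The downside is the chance of an unneeded pause: with the illustrative counts, about 2.5% if the true acute grade 3+ rate is 0.8%, and 5.3% if it is 1%.
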